To assess the pharmacokinetics (PK) of peposertib	Pharmacokinetic profile of peposertib in terms of PK parameter estimates (e.g. C_{max} , AUC_{0-t} , t_{max} , CL/f , Vz/f , and $t_{1/2}$)	Fraction day (FD)1 and FD9

Overall Design: This is a multicenter, open-label, single arm, dose escalation study in participants with locally advanced rectal cancer.

The study will consist of a Screening period of 4 weeks, a Treatment period of 5 to 5.5 weeks (25 or 28 FD) (DLT period), a Short-term Safety Follow-up period of 13.5 weeks (including 30 days after surgery), a Long-term Safety Follow-up period until 1 year after the start of study intervention/randomization.

Number of Participants: The planned cohort size is 3 participants. The total sample size will depend on the number of cohorts to be evaluated. It is anticipated that 18 to 30 evaluable participants will be required.

Study Intervention Groups and Duration: Participants will be assigned to peposertib given in combination with capecitabine 825 mg/m² twice daily 5 days/week and RT of 50 to 50.4 Gy to the tumor area and 45 Gy to the electively irradiated tissues in 25 or 28 fractions (corresponding to 5 to 5.5 weeks). The starting dose of peposertib for the first cohort will be 50 mg once daily 5 days/week. The peposertib dose for the next cohorts will be determined by the Safety Monitoring Committee (SMC) guided by a Bayesian 2-parameter logistic regression model with overdose control.

[figure not shown]
Premature Discontinuation: As of 06 May 2021, in the Phase Ib dose escalation part, 19 participants have been treated with doses ranging from 50 to 250 mg peposertib once daily plus capecitabine and RT. Preliminary clinical data from 16 participants that have finished the study up to Week 19 as well as changing treatment landscape in locally advanced rectal cancer indicate that the ability to generate a meaningful proof of concept under the current protocol is low. Therefore, the dose escalation in the Phase Ib part will be prematurely discontinued after completing the Cohort 5 of 150 mg, and the Phase II part of the study will not be initiated.

Involvement of Special Committee(s): Yes

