4.1.2 Treatment Period

The starting dose of peposertib for the first cohort will be 50 mg once daily (Section 4.3). Participants for next cohorts will be assigned to an peposertib dose determined by the SMC. The SMC dose recommendations will be guided by a Bayesian 2-parameter logistic regression model with overdose control (Appendix 10). The planned cohort size is 3 participants. Peposertib will be given in combination with capecitabine at a dose of 825 mg/m² twice daily and RT of 50 to 50.4 Gy to the tumor area and 45 Gy to the electively irradiated tissues in 25 or 28 fractions (corresponding to 5 to 5.5 weeks). Full details of the dosing regimens are provided in Section 6.6.2.

After each cohort has completed the 5 to 5.5-week treatment period (DLT period), the SMC will review safety, including DLT data, tolerability, and PK data if available, and will recommend the peposertib dose for the next cohort. In addition, any toxicities observed during the Short-term Safety Follow-up will be reviewed and considered by the SMC for the overall evaluation of the safety and proposal of dose escalation of peposertib. Dose limiting toxicities are defined in Section 6.6.1. If the SMC decides to escalate the dose for the next cohort, it is in exceptional cases at discretion of the study team (medical lead and safety lead with input from statistician) to include up to 3 further participants in parallel, on a dose level that has already been tested in a previous cohort.

Participants will receive CRT until treatment completion after 25 or 28 RT fractions or disease progression, unacceptable toxicity or participant refusal to continue.

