7.2 Participant Discontinuation/Withdrawal from the Study

- A participant may withdraw from the study at any time, at his/her own request or may be withdrawn at any time at the discretion of the Investigator for safety, behavioral, compliance, or administrative reasons.
- At the time of discontinuing from the study, if possible, a discontinuation visit will be conducted, as listed in the SoA. The SoA specifies the data to collect at study discontinuation and follow-up, and any additional evaluations that need to be completed.
- If the participant withdraws consent for future involvement in the study, any data collected up to that point may still be used, but no future data can be generated, and any biological samples collected will be destroyed.
- A participant has the right at any time to request destruction of any biological samples taken. The Investigator must document this in the site study records.

Participants should be explicitly asked at time of discontinuation of study if they would allow survival information to be collected including verification of medical/public records as permitted by local regulations. These responses should accordingly be captured in the participant's source data and reported in the eCRF accordingly.

The SoA (Section 1.3) specifies the data to collect at study discontinuation and follow-up, and any additional evaluations that need to be completed.

Participants who are discontinued/withdrawn from the study will not be replaced.

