- Procedures conducted as part of the participant's routine medical care (e.g. blood count) and obtained before signing of the ICF may be used for Screening or baseline purposes provided the procedures met the protocol-specified criteria and were performed within the time frame defined in the SoA (Section 1.3).
- Regarding the visits from Week 7 to 14 during the short-term safety follow-up ([Table 1](#)). The Week 14 visit is mandatory as this is needed for restaging and evaluation. All other visits in this period are optional and needed only in case of acute toxicities until recovery to Grade 1 or baseline.
- A maximum of 255 mL of blood will be collected in any one-month period from each participant in the study, including any extra assessments that may be required.

Screening:

Participants will be screened between Days -28 and -1, prior to first dosing on Day 1. Assessments and procedures to be performed at Screening are detailed in the SoA (Section 1.3). Screening-specific procedures include:

- **Demography:** date of birth, sex (gender), race, and ethnicity.
- **Medical history:** disease history, previous illness and surgeries (e.g. all during the past year and only major ones prior to that), concomitant illness, relevant medication, allergies, therapies stopped or changed at entry into the study, tobacco use including pack years, and alcohol use.
- **Eastern Cooperative Oncology Group Performance Status:** assessed at Screening to assess eligibility (Section 5.1) and then assessed according to the SoA (Section 1.3).
- **Chest-abdominal computerized tomography (CT):** A CT scan of the chest and abdomen will be performed prior to the beginning of study intervention to document the baseline status of the participant. Computerized tomography will be performed with intravenous iodinated contrast unless contraindicated. Evaluation up to 28 days prior to start of study intervention is allowed.

In the case of a rescreen and the screening CT scan is > 28 days from the previous screening scan, the screening CT will need to be repeated.

- **DRE and endoscopy (and EUS if indicated or if performed):** for participants who have received induction chemotherapy prior to start of study

Surgery

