9.2 Sample Size Determination

A Bayesian 2-parameter logistic regression model with overdose control is applied to assist the SMC in dose recommendations. The planned cohort size is 3 participants. The total sample size will depend on the number of cohorts to be evaluated. It is anticipated that 18 to 30 evaluable participants are required.

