8.2 Definition of Analysis Populations and Subgroups

The analysis populations are specified below:

Table 1 Description of Analysis Sets

Population	Description
Enrolled	All participants who sign informed consent
Dose escalation (DE)	The DE Analysis Set will include all participants treated in dose escalation cohorts, who receive at least 80% of peposertib, 50% of capecitabine, and 80% of RT planned dose and complete the DLT period (5 or 5.5 weeks after start of treatment or for the entire duration of the treatment). The DE set will also include participants treated in dose escalation cohorts who experience a DLT during the DLT period regardless of the amount of each study intervention received/completion of the DLT period.
Full analysis set (FAS)	The FAS will include all participants who are enrolled in the study and received at least 1 dose of study intervention.
Safety (SAF)	The SAF analysis set will include all participants who receive at least 1 dose of study intervention. Participants will be analyzed according to the actual treatment they receive. In case of different doses received the dose with high number of administrations will be used as actual treatment.
Pharmacokinetics (PK)	The PK analysis set is defined as all participants who receive at least 1 dose of peposertib and have sufficient peposertib plasma concentration data to enable the calculation of at least 1 PK parameter. Sufficient concentration data is defined as at least 3 valid, post dose, concentration points in the PK profile to obtain any PK parameter.

DE=dose escalation, DLT=dose limiting toxicity, FAS=full analysis set, PK=pharmacokinetic, RT=radiotherapy, SAF=safety

Table 2 Summary of Analyses and associated Analysis Set

Analyses	ENR	SAF	FAS	DE	PK
Disposition	✓				
Baseline assessments		✓			
Past and concomitant therapies		✓			
Compliance and exposure		✓			
Primary endpoint: DLTs				✓	
Efficacy			✓		
Safety and tolerability		✓			
CCI					
Pharmacokinetics					✓
CCI					

DE=dose escalation, ENR=enrolled, FAS=full analysis set, PK=pharmacokinetic, SAF=safety

9 General Specifications for Data Analyses

Study intervention groups

Unless otherwise indicated all analyses will be presented separately for each dose level, and overall.

Data handling after cut-off date

Data after cut-off do not undergo the cleaning process, will not be included in SDTMs, and will not be displayed in any listings or used for statistical analyses or imputation.

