Stop dates are not affected by this rule, e.g. a stop date of AEs, which starts prior to the cut-off, but stops after date of cut-off, will not be changed.

Significance level

All statistical tests mentioned in this IAP are to be regarded as exploratory. All statistical tests comparing study intervention groups will be performed two-sided. If confidence intervals are to be calculated, these will be two-sided with a confidence probability of 95%, unless otherwise specified in the corresponding section of this IAP.

Presentation of continuous and qualitative variables

Continuous variables will be summarized using descriptive statistics, i.e.

- number of participants, number of participants with non-missing values,

- mean, standard deviation,
- median, 25th Percentile - 75th Percentile (Q1-Q3),
- minimum, and maximum.

Qualitative variables will be summarized by counts and percentages.

Unless otherwise stated the calculation of proportions will be based on the number of participants in the analysis population of interest. Therefore, counts of missing observations will be included in the denominator and presented as a separate category.

For summaries by visits, only visits where all subsequent visits have 3 or more participants will be displayed. In case the analysis refers only to certain visits, percentages will be based on the number of participants in the corresponding analysis set.

Presentation of PK concentration data

Peposertib, its metabolite (if available), capecitabine, and its metabolite (if available) concentration data will be descriptively summarized using: number of non-missing observations (n), arithmetic mean (Mean), standard deviation (Sd), coefficient of variation (CV%), minimum (Min), median (Median), and maximum (Max). If $n \leq 2$, only n, Min, and Max will be reported.

Descriptive statistics of PK concentration data will be calculated using values with the same precision as the source data, and rounded for reporting purposes only. The following conventions will be applied when reporting descriptive statistics of PK concentration data:

Mean, Min, Median, Max: 3 significant digits

Sd: 4 significant digits

CV%: 1 decimal place

Presentation of PK parameter data

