15.6.2 ECG and QT/QTc Evaluations

Population: SAF analysis set

Electrocardiogram values based on the “Electrocardiogram” eCRF section will be used for summary statistics and shift tables.

ECG parameters (Heart Rate, R-R duration, PQ/PR duration, QT duration, QR duration, QTcF) will be summarized by dose level and visit, using descriptive statistics (see [Section 9](#)) for absolute values and absolute change from baseline.

The number of participants with normal ECGs at baseline and abnormal ECGs post baseline will be calculated by visit and summarized in a frequency table by dose level and overall. In addition, ECG parameters on treatment will be presented by the following frequency table (by dose level and overall):

- Shift from normal baseline result to the worst on-treatment value
 - ≤ 450 ms
 - > 450 ms and ≤ 480 ms
 - > 480 ms and ≤ 500 ms
 - > 500 ms
- Worst on treatment mean QTcF increase from baseline
 - ≤ 30 ms
 - > 30 ms and ≤ 60 ms
 - > 60 ms

If duplicate/triplicate measurements are performed at any time point, the following will apply:

- For quantitative parameters, the mean of the triplicate measurement will be used as summary
- For results interpretation, the worst Overall conclusion will be retained.

Visits and time points to be displayed in summary tables are all scheduled visits where ECG assessments are performed.

Two listings will display all the results as presented in “ECG” eCRF page, one on qualitative results and another one on quantitative results. All visits, time points, flag for pre /on /post treatment, and, in case of triplicates, mean for quantitative results and worst overall conclusion for qualitative results, will be included in listings.

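### SAP section 9 shows a visit only if every later visit has at least 3 participants, so in a 3-participant dose level one thin later visit can hide complete on-treatment visits in the laboratory by-visit displays and vital-sign plots

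*SAP*

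**What the plan says.** SAP section 9, under the presentation of continuous and qualitative variables, sets the rule for summaries by visit: "only visits where all subsequent visits have 3 or more participants will be displayed". It sets no condition on the count at the visit itself and does not say whether the 3 is counted per dose level or overall. Earlier in the same section the default layout is given: "Unless otherwise indicated all analyses will be presented separately for each dose level, and overall".

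The counts it acts on are small. Protocol 9.2: "The planned cohort size is 3 participants". Protocol 7.2: "Participants who are discontinued/withdrawn from the study will not be replaced". A dose level can be larger, because Protocol 4.1.2 allows the study team, exceptionally, to "include up to 3 further participants in parallel, on a dose level that has already been tested in a previous cohort".

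Follow-up visits enter the rule. SAP 15.4 puts all assessments, not only those on treatment, into the laboratory summaries by visit. Protocol section 8 makes Week 14 mandatory in the Week 7 to 14 period and says of the rest: "All other visits in this period are optional and needed only in case of acute toxicities until recovery to Grade 1 or baseline". Protocol Table 1 schedules vital signs, hematology and chemistry in that column.

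**The concern.** A minimum-count rule normally drops a visit because that visit has too few participants. This one drops a visit because some other, later visit has too few. A complete FD1 column disappears when Week 52 is thin, while the last visit always passes, even with n = 1, because nothing follows it.

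The design makes thin later visits likely: cohorts of 3, no replacement, a year of follow-up, and optional visits attended only by participants with acute toxicity. What is at stake is the display of laboratory values and vital signs over time by dose level, which supports the secondary safety objective. A programmer must either deliver tables without the treatment period or depart from the SAP without documentation.

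**Working it through.** The plan gives no figure to reproduce. The check applies the rule literally and compares it with a rule that uses each visit's own count.

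**Inputs.** The laboratory schedule in Protocol Tables 1 and 2 has 13 visits: Screening, FD1, FD6, FD11, FD16, FD21, FD25/28, and Weeks 14, 19, 21, 27, 39 and 52. The dose level has 3 participants. Loss and attendance rates are assumptions, because the documents give none.

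**Rules.** With n_i participants at visit i:
- Literal: show visit i if n_j ≥ 3 for all j > i.
- Own count: show visit i if n_i ≥ 3.

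| Dose level of 3 | Literal | Own count |
|---|---|---|
| No loss, no optional visit | 13 of 13 | 13 of 13 |
| One participant absent at Week 52 only | 1 of 13 (Week 52, n = 2) | 12 of 13 |
| One participant lost before Week 19 | 1 of 13 (Week 52, n = 2) | 8 of 13 |
| No loss, one optional visit with n = 1 | 7 of 14 (the n = 1 visit and Weeks 14 to 52) | 13 of 14 |

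In the last row the 7 hidden visits are Screening to FD25/28.

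**How often a thin last visit arises.** If each participant is lost by the last visit with probability d, the chance that fewer than 3 of 3 remain is 1 − (1 − d)³. For d = 5%, 10%, 20% and 30% this is 14%, 27%, 49% and 66%. With 4 in the dose level, 1 − [(1 − d)⁴ + 4d(1 − d)³] gives 1%, 5%, 18% and 35%. With 6 it is at most 7%, and with all 19 treated about 0%.

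**How often a given optional week is thin.** If each of 3 participants attends with probability q, the chance that 1 or 2 attend is 3q(1 − q)² + 3q²(1 − q) = 3q(1 − q). For q = 30%, 50% and 70% this is 63%, 75% and 63%; for 10% and 90% it is 27%. This matters only if optional weeks are tabulated as separate visits.

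**A route without dropout.** The primary analysis is cut off when the last participant reaches the end of short-term follow-up, about Week 19 (SAP 6.3). Week 21 is nominally two weeks later. If that participant's dose-level peers started a few weeks earlier, Week 21 can hold 1 or 2 participants at the cut-off, which hides every earlier visit. The start dates are not given.

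**Outputs reached.** Laboratory summaries by visit and boxplots by time point (SAP 15.4) and vital-sign line plots (SAP 15.5) run by visit. The DLT, adverse event, death, shift, worst-value and liver tables do not.

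**The case against.** **ECG.** SAP 15.6.2 says ECG parameters "will be summarized by dose level and visit", and a reader might infer that these tables are blanked too. They are not. The same section requires every scheduled visit with an ECG to be displayed, and that specific rule governs. ECGs are also scheduled only at Screening, FD1, FD11 and FD25/28, so neither long-term loss nor an optional visit could reach them.

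**Scope.** A reader might infer that most on-treatment safety summaries vanish. The documents do not support this. The main safety tables are not by visit, full listings are planned, and outputs for the safety monitoring committee have their own analysis plan.

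**Size.** It is tempting to quote 97% to 66% for a thin optional week (1 − 0.3³ and 1 − 0.7³). That counts weeks with no attendee, which have no visit to tabulate; at 30% attendance such weeks have probability 0.7³ = 34%. It is equally tempting to quote 85% for the six visits from Week 14 on (1 − 0.9¹⁸), but that rests on a single assumed missingness rate, independent across visits of the same person. Nor does the text support blanking in nearly all cohorts. The synopsis reports that, as of 6 May 2021, "19 participants have been treated with doses ranging from 50 to 250 mg peposertib once daily", and names Cohort 5 as the last: 19/5 = 3.8 per cohort on average, so some dose levels probably exceed 3.

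**Counting level.** If the 3 is counted overall, scheduled visits are essentially safe. Optional weeks are not: with 19 participants, the chance that exactly 1 or 2 attend, 19q(1 − q)¹⁸ + 171q²(1 − q)¹⁷, is 56%, 57% and 22% at q = 5%, 10% and 20%. Table 1, however, has one Week 7 to 14 column, and the SAP does not say that optional weeks form separate analysis visits.

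**Intent.** The authors may have meant an own-count rule, or a cut of the sparse tail. SAP small-sample rules for PK do use the own count, which supports that reading. It remains an inference, and nothing in the SAP corrects the sentence.

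What stands after this is the wording defect and its effect on the laboratory and vital-sign by-visit displays.

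**Conclusion.** The rule is wrong as written. In a dose level of 3, counted per dose level, one absence at a later visit, or one separately tabulated optional visit with 1 or 2 attendees, removes every earlier visit from the laboratory by-visit summaries and boxplots and the vital-sign line plots. The last visit stays whatever its size. The mechanism follows from the text alone; its frequency rests on assumed loss and attendance.

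The effect is conditional. Complete follow-up with no thin optional visit costs nothing, and larger dose levels are much less exposed to loss. This is a reporting defect: no data are lost and the DLT endpoint is untouched. It still merits correction, because the rule can suppress complete treatment-period columns and the repair is simple.

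**What to change.** Replace the sentence in SAP section 9 with, for example:

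> In by-visit summaries, scheduled visits at which at least 3 participants overall have data will be displayed for all dose levels (where a dose level has n ≤ 2, only n, minimum and maximum are shown); optional Week 7-13 and unscheduled visits are listed only.

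This ties display to the visit's own count, fixes the counting level, keeps the same visits across dose levels, and avoids means on 1 or 2 participants in the way the SAP already does for PK. In the Week 52 example all 13 visits would appear, with Week 52 reduced to n, minimum and maximum for that dose level, provided at least 3 participants overall attend Week 52. The cost is one SAP sentence and no new data.

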10.1 Disposition of Participants and Discontinuations

All tables and listings related to disposition of participants and discontinuations will be generated using Enrolled analysis set.

A primary table of subject disposition will provide the overall summary of the analysis sets by dose level and overall:

- Number of screened participants (will be reported in the overall column only)
- Number of participants discontinued prior to treatment start (overall and by reason) (will be reported in the overall column only)
- Number of participants who continued beyond screening
- End of treatment status for peposertib with:
 - Number of participants who did not receive peposertib (“M3814/PLACEBO ADMINISTRATION DETAILS” eCRF Page)
 - Number of participants with ongoing peposertib administration (“M3814/PLACEBO ADMINISTRATION DETAILS” and “M3814/PLACEBO TERMINATION” eCRF Page)

- Number of participants who completed treatment with peposertib (“M3814/PLACEBO TERMINATION” eCRF Page)
- Number of participants who discontinued from peposertib overall and by reason (“M3814/PLACEBO TERMINATION” eCRF Page)
- End of treatment status for RT with:
 - Number of participants who did not receive RT (“RADIOTHERAPY ADMINISTRATION” eCRF Page)
 - Number of participants with ongoing RT administration (“RADIOTHERAPY ADMINISTRATION” and “RADIOTHERAPY TERMINATION” eCRF Page)
 - Number of participants who completed treatment with RT overall and by reason (“RADIOTHERAPY TERMINATION” eCRF Page)
 - Number of participants who discontinued from RT overall and by reason (“RADIOTHERAPY TERMINATION” eCRF Page)
- End of treatment status for capecitabine with:
 - Number of participants who did not receive capecitabine (“CAPECITABINE ADMINISTRATION” eCRF Page)
 - Number of participants with ongoing capecitabine administration (“CAPECITABINE ADMINISTRATION” and “CAPECITABINE TERMINATION” eCRF Page)
 - Number of participants who completed treatment with capecitabine overall and by reason (“CAPECITABINE TERMINATION” eCRF Page)
 - Number of participants who discontinued from capecitabine overall and by reason (“CAPECITABINE TERMINATION” eCRF Page)
- Number of participants who underwent rectal surgery at week 15 (“RECTAL SURGERY AT WEEK 15” eCRF page)
- End of study status with:
 - Number of participants with peposertib, RT and/or capecitabine administration ongoing
 - Number of participants off all treatments and in follow-up, and for those, the number of participants last known to be alive within 3 months before the cut-off date and the number of participants last known to be alive more than 3 month prior to the cut-off date (all ADMINISTRATION and TERMINATION related eCRF pages and “STUDY TERMINATION” eCRF pages)
 - Number of participants who discontinued or completed trial overall and by reason (“STUDY TERMINATION” eCRF page)

A second summary table on analysis sets will be generated:

- Number of participants in Enrolled population (overall only)
- Number of participants in FAS analysis set
- Number of participants in SAF analysis set
- Number of participants in DE analysis set
- Number of participants in PK analysis set

A third summary table will display the number of participants overall, in each country and in each site (per analysis set).

A listing of subject disposition will include the following information (as applicable): Dose level, subject identification number, date of informed consent form (ICF), rectal surgery at 15 weeks flag and date, reason for screen failure, date of first and last dose, FAS/SAF analysis set, DE analysis set and PK analysis set.

A second listing will include the following study termination information: Dose level, subject identification number, end of trial status (completed, ongoing, discontinued), the reason for termination of the trial, the date of trial termination, time on trial (time from ICF signature to end of trial), and the date of first and last dose of peposertib, RT and capecitabine.

A third listing will include the following peposertib termination information: Dose level, subject identification number, end of treatment status (completed, ongoing, discontinued), the reason for peposertib termination, and the date of first and last dose.

A fourth listing will include the following RT termination information: Dose level, subject identification number, end of treatment status (completed, ongoing, discontinued), the reason for RT termination and the date of first and last dose.

A fifth listing will include the following capecitabine termination information: Dose level, subject identification number, end of treatment status (completed, ongoing, discontinued), the reason for capecitabine termination, and the date of first and last dose.

In addition, for the assessment of COVID-19 impact on this study, a listing will include the following information (as applicable): Formulation, dose level, subject identification number, date of first and last dose, pandemic start date in the country, if DLT or any FUP periods were potentially affected by pandemic, if any COVID-19 related AE or PD occurred during the pandemic period.

